10.5 Windowing Conventions

All scheduled study visits are defined relative to Study Day 1, the date of first dose. Scheduled visit windows are defined in [Appendix 3](#). A windowing convention will be used to determine the analysis visit value for a given measurement and will be applicable for all by-visit summaries and analyses for efficacy and safety data. Refer to [Table 2](#) below for specific visit windows.

Table 2 Visit Windows for Efficacy and Safety Analyses

| For all Efficacy (Except for QoL) and PD Analyses | |
|---|--|
| Scheduled Study Visit (Protocol Scheduled Day) | Analysis Visit Window (Study Day) |
| Baseline | ≤ 1 |
| Week 4 (Day 28 ± 5) | 2 to 43 |
| Week 8 (Day 56 ± 5) | 44 to 71 |
| Week 12 (Day 84 ± 5) | 72 to 99 |
| Week 16 (Day 112 ± 7) | 100 to 141 |
| Week 24 (Day 168 ± 7) | 142 to 211 |
| Week 36 (Day 252 ± 7) | 212 to 309 |
| Week 52 (Day 364 ± 7) | ≥ 310 |
| For QoL Analysis | |
| Scheduled Study Visit (Protocol Scheduled Day) | Analysis Visit Window (Study Day) |
| Baseline | ≤ 1 |
| Week 4 (Day 28 ± 5) | 2 to 57 |
| Week 12 (Day 84 ± 5) | 58 to 127 |
| Week 24 (Day 168 ± 7) | 128 to 211 |
| Week 36 (Day 252 ± 7) | 212 to 309 |
| Week 52 (Day 364 ± 7) | ≥ 310 |
| For Safety Analysis | |
| Scheduled Study Visit (Protocol Scheduled Day) | Analysis Visit Window (Study Day) |
| Baseline | ≤ 1 |
| Week 1 (Day 7 ± 2) | 2 to 15 |
| Week 4 (Day 28 ± 5) | 16 to 43 |
| Week 8 (Day 56 ± 5) | 44 to 71 |
| Week 12 (Day 84 ± 5) | 72 to 99 |
| Week 16 (Day 112 ± 7) | 100 to 127 |
| Week 20 (Day 140 ± 7) | 128 to 155 |
| Week 24 (Day 168 ± 7) | 156 to 190 |
| Week 30 (Day 210 ± 7) | 191 to 232 |
| Week 36 (Day 252 ± 7) | 233 to 274 |
| Week 44 (Day 308 ± 7) | 275 to 337 |

| For Safety Analysis | |
|---|--|
| Scheduled Study Visit (Protocol Scheduled Day) | Analysis Visit Window (Study Day) |
| Week 52 (Day 364 ± 7) | 338 to 379 |
| Week 56 (Day 392 ± 7) | ≥ 380 |

Windowing will be applied prior to any missing data calculations. The last non-missing measurement taken prior to the date of first dose (including unscheduled assessments) will be labeled as “Baseline”. Unscheduled or Screening visits that occurred before the baseline visit will not be assigned an analysis visit. The early discontinuation visit will be eligible for allocation to an analysis visit.

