13.5.3.2.1 Analysis and Imputation Methods

HbF responder rate (as defined by the proportion of subjects with an absolute increase of $\geq 3\%$ from baseline) at Week 24 will be assessed using a stratified Cochran-Mantel-Haenszel (CMH) test adjusted for stratification factors of region (North America/Europe vs. Africa/Middle East) and HU use (Yes vs. No). The ITT set will be used for this analysis.

The frequency and percentage of responders and non-responders at Week 24 will be presented for each treatment group as well as ORs, RRs, 95% Cis, and p-values from the CMH test comparing active groups to placebo.

Bar plots will be provided, and the proportion of subjects with response in HbF in each treatment group, Odds ratios, 95% CI, and p values will be displayed for each treatment comparison.

The following imputation rules will be applied for the key secondary efficacy endpoint (HbF responder at Week 24):

1. Subject will be treated as a non-responder if there is an initiation of HU post randomization and prior to Week 24.
2. If HbF value is missing at Week 24, the HbF value at Week 16 will be used for the analysis. If HbF value at Week 16 is also missing, subject will be treated as a non-responder.
3. Any HbF value within 8 weeks (56 days) of a RBC transfusion will be excluded from all analyses. If the subject does not have a valid HbF value at Week 24 and/or Week 16, subject will be treated as a non-responder.

Number of subjects with imputed values for the key secondary efficacy endpoint and the reason for imputation (imputed as non-responder because of initiation of HU post randomization, imputed with Week 16 value because of Week 24 value is missing, imputed from the last post-baseline assessment prior to RBC transfusion) will also be summarized. The observed and imputed Week 24 HbF values will both be summarized for the by-visit analysis.

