Annualized rate of days hospitalized for VOC-related hospitalization will be analyzed in the same way as annualized rate of VOC-related hospitalization.

Time to first for VOC-related hospitalization

The time to first VOC-related hospitalization event will be analyzed using Kaplan-Meier methods. Time in months to the first VOC-related hospitalization event can be calculated as ([date of first VOC-related hospitalization event – date of first dose + 1] / 30.4375).

Time to second VOC

This analysis of time to second VOC event will be analyzed using Kaplan-Meier methods similar to the analysis of the time to first VOC. A patient with less than two VOCs before withdrawal or completion of the study is considered censored at the time of withdrawal or completion of the study.

A sensitivity analysis will be performed separately, excluding these subjects without any VOCs.

HbF responder rate (as defined by proportion of subjects with an absolute increase of $\geq 3\%$ in HbF from baseline) at Week 52

This analysis of HbF responder at Week 52 will be similar to the HbF responder rate analysis at Week 24 ([Section 13.5.3.2](#)). Similar imputation rules will apply:

1. Subject will be treated as a non-responder if there is an initiation of HU post randomization and prior to Week 52.
2. HbF value from Week 36 (the last scheduled visit before the target analysis visit) will be used when Week 52 value is missing,
3. Any HbF value within 8 weeks (56 days) of RBC transfusion is excluded from all analyses.

Change from baseline in HbF (%) and F-cells (%) at Week 24 and Week 52

Change and percentage change from baseline in HbF (%) and F-cells (%) will be analyzed using mixed models for repeated measures (MMRM) with baseline value as a covariate, fixed effects for region (North America/Europe vs. Africa/Middle East), HU use (yes vs. no), treatment, visit, and treatment-by-visit interaction. Unstructured covariance matrices will be assumed for all models, but auto-regressive 1 (AR1) and compound symmetry (CS) may also be assessed (in that order) if the unstructured covariance matrix does not converge.

Values used at the visit and change from baseline for each parameter will be summarized for each post-baseline timepoint. The LS Mean estimates and 95% CIs will be displayed for all treatment groups. LS Mean difference estimates and 95% CIs with p-values for all IMR-687 treatment groups (relative to placebo) will be provided.

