Line plots will be provided for LS mean change from baseline +/- standard error (SE) at each post-baseline visit by treatment group.

Waterfall plots will be provided for change in HbF (%) from Baseline to Week 24 and from Baseline to Week 52 by treatment group, respectively. The plot of individual subjects change from baseline will be displayed with a reference line at 3%.

If the HbF value at Week 24 and Week 52 were imputed from the previous visits in the responder analysis, the imputed value will also be used for the MMRM, summary statistics and waterfall plots. The observed value and imputed value will both be presented in the data listing.

Hb responder rate (as defined by proportion of subjects with an absolute increase of ≥ 1.0 g/dL in total Hb from baseline) at Week 24 and Week 52

This analysis of Hb responder rate at Week 24 and Week 52 will be similar to the HbF responder rate analysis at Week 24 and 52. The same imputation rules will apply.

Change from baseline in total Hb (g/dL) at Week 24 and Week 52

The analysis of total Hb (g/dL) at Week 24 and Week 52 will be similar to Change (and percentage change) from baseline in HbF (%) at Week 24 and 52.

Change from baseline in biomarkers of RBC hemolysis (% and absolute reticulocytes, unconjugated [indirect] bilirubin, and LDH) at Week 24 and Week 52

The analysis of change (and percentage change) from baseline in biomarkers of RBC hemolysis at Week 24 and Week 52 will be similar to the analysis of other change from baseline efficacy variables. The analysis will be performed for each of the following parameters, at Week 24 and Week 52 separately:

- % Reticulocytes
- Absolute Reticulocytes
- Unconjugated [indirect] Bilirubin
- Lactate dehydrogenase (LDH)

Line plots will be provided for LS mean change +/- SE.

Change from baseline in each measured subdomain of the ASCQ-Me questionnaire at Week 24 and Week 52

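### HbF values carried forward from Week 16 or Week 36 enter the MMRM as Week 24 or Week 52 data although the source visit is already in the model; the bias is small and depends on the time course

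*SAP*

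**What the plan says.** The carry-forward rules belong to the responder endpoints. SAP 13.5.3.2.1: "If HbF value is missing at Week 24, the HbF value at Week 16 will be used for the analysis". For the Week 52 responder rate, SAP 13.5.4: "HbF value from Week 36 (the last scheduled visit before the target analysis visit) will be used when Week 52 value is missing". Transfusion opens a second route to a missing value: "Any HbF value within 8 weeks (56 days) of a RBC transfusion will be excluded from all analyses".

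The change-from-baseline text in SAP 13.5.4 then extends the fill-in. Where a Week 24 or Week 52 HbF value was imputed for the responder analysis, "the imputed value will also be used for the MMRM, summary statistics and waterfall plots".

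The source visits are separate analysis visits in SAP 10.5, Table 2: "Week 16 (Day 112 ± 7) | 100 to 141" and "Week 36 (Day 252 ± 7) | 212 to 309". The MMRM has visit and treatment-by-visit terms, "Unstructured covariance matrices will be assumed for all models", and the output is "LS mean change from baseline +/- standard error (SE) at each post-baseline visit by treatment group".

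For total Hb, SAP 13.5.4 says the responder analysis follows the same imputation rules and the change analysis is similar to the HbF one. No carry-forward rule names F-cells. Protocol 13.4 describes the MMRM without any carry-forward.

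**The concern.** A likelihood-based MMRM already uses a subject's observed visits to inform a missing one. If the Week 16 value is also entered as Week 24, the model sees two rows where there was one measurement. It treats the second as fresh information on the target visit, with two consequences:

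- The target-visit mean moves towards the earlier visit.
- The standard error falls below what the observed data support.

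The results affected are tested. HbF and F-cell change and total Hb change are steps 9 and 11 of the interim hierarchy (SAP 12.3) and steps 10 and 12 of the final one (SAP 12.4). HbF change is also the direct readout of the drug's intended mechanism. The imputation-rule sensitivity analyses in SAP 13.5.3.2.2 cover only the HbF responder rate, and no observed-data MMRM is specified for the ITT set.

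**Working it through.** The documents give no figure for the HbF or Hb change analysis, so there is none to reproduce. The check has three parts.

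**1. How many values are copies**

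Inputs from the documents:
- 20% dropout before Week 24 (Protocol 13.7) and a 25% dropout scenario (SAP 8.1.2).
- Efficacy windows (SAP 10.5): Week 16 = Days 100–141, Week 24 = Days 142–211, Week 36 = Days 212–309, Week 52 = Day 310 onward.
- Windowing comes before missing-data handling, and an early discontinuation visit can be allocated to a window.
- A subject with no Week 16 value has nothing to carry and is only classed as a non-responder.

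Assumption: dropout is spread evenly over time.

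Week 24 copies, as a share of randomised subjects:
- Early-termination visit done: only exits on Days 100–141 (42 days) lead to a copy. 20% × 42/168 = 5.0%.
- No such visit: exits between Day 112 and Day 168 (56 days). 20% × 56/168 = 6.7%.

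Week 52 copies:
- Visit done: exits on Days 212–309 (98 days). 25% × 98/364 = 6.7%.
- No visit: exits between Day 252 and Day 364 (112 days). 25% × 112/364 = 7.7%.

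As a share of the rows actually present at Week 24 the figures are a little higher:
- Visit done: exits on Days 1–99 leave no row, 20% × 99/168 = 11.8%, so 5.0/88.2 = 5.7%.
- No visit: exits up to Day 112 leave no row, 20% × 112/168 = 13.3%, so 6.7/86.7 = 7.7%.

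The two dropout rates are used separately and are not one curve: 25% spread evenly over 364 days puts 25% × 168/364 = 11.5% before Week 24. Missed visits and transfusion exclusions add copies in a number the documents do not give.

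**2. Bias in the treatment difference**

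With equal missingness in both arms:

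bias = share carried forward × (effect at earlier visit − effect at target visit)

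- Week 24, Week 16 response assumed to be 60–80% of the Week 24 response: attenuation from 5.0% × 0.20 = 1.0% to 6.7% × 0.40 = 2.7%. With the row-based shares it is 5.7% × 0.20 = 1.1% to 7.7% × 0.40 = 3.1%.
- Week 52, effect assumed to rise linearly to 3.0 HbF points: the Week 36 effect is 3 × 36/52 = 2.08. Bias is 6.7% × (2.08 − 3.00) = −0.06 to 7.7% × (2.08 − 3.00) = −0.07.
- Plateau from Week 16: zero.
- Waning effect, assumed 1.17 at Week 36 and 0.50 at Week 52: 6.7% to 7.7% × 0.67 = about +0.05, in the drug's favour.

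**3. Simulation of the mechanism**

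The settings were 31 placebo and 49 higher-dose subjects (SAP 8.1), seven visits, an unstructured-covariance likelihood fit and 600 runs per scenario. Assumed: SD of change 3 HbF points, and within-subject correlation falling from 1 towards 0.5. Copying was set well above part 1: 20% missing at Week 24 and 25% at Week 52, with the earlier value always available.

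| Scenario, Week 52 | True | Formula | Carry-forward bias | Observed-only bias |
|---|---|---|---|---|
| Rising | 3.00 | −0.23 | −0.22 | +0.01 |
| Plateau | 2.00 | 0 | +0.01 | −0.01 |
| Waning | 0.50 | +0.17 | +0.22 | +0.06 |

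Simulation error is about 0.03. The gap between the two fits (−0.23, about +0.01, +0.16) agrees with the formula.

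The mean model standard error fell from about 0.70 to 0.685 at Week 24 (about 3%) and from about 0.73 to 0.685 at Week 52 (about 6%). Interval coverage in the carry-forward fit was 93% to 97%. Its model standard error stayed close to the actual spread of its estimates.

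**The case against.** The strongest case against acting is that the effect is small, partly checked, and low in the hierarchy. Much of this stands.

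- **Size.** A reader might take the 20% dropout at face value and infer that one in five Week 24 values is a duplicate, with attenuation of 0.20 × 0.20 = 4% to 0.20 × 0.40 = 8%. The SAP's rules do not support that. Early leavers have nothing to carry, and an early-termination sample from Day 142 onward is a real Week 24 observation. Reaching one in five through dropout would need every exit to fall in the Week 16 interval.
- **Certainty of bias.** A reader might infer that the mean change is necessarily biased, or always against the drug. The documents give no HbF time course; the bias is nil on a plateau and can take either sign.
- **Error bars.** A reader might infer intervals that are materially too narrow. Even with 20 to 25% copied, the shrinkage was 3 to 6% and coverage stayed near nominal.
- **Reach.** The sentence that feeds the MMRM names HbF only. Total Hb is reached by inference from two cross-references. Hb is also sampled at Weeks 20 and 30, and some of those samples can fall in the Week 24 window, so missing Hb should be rarer.
- **Safeguards.** Observed and imputed Week 24 HbF are both summarised, and both values are listed. Table 7 names the per-protocol set as a sensitivity set for this MMRM, and SAP 13.5.3.2.2 rules out imputation there, though it says so under the responder endpoint.

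None of this gives a reason to enter the copy. The safeguards do not supply an ITT model fitted to observed data.

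**Conclusion.** The point holds as a modest analysis flaw. The SAP expressly puts a carried-forward HbF value into a repeated-measures model that already contains the source measurement; total Hb appears to follow. Under even dropout at the documents' rates, about 5 to 7% of subjects would have a copied Week 24 value and 7 to 8% a copied Week 52 value, before an unknown addition from missed or transfusion-excluded samples. Attenuation at Week 24 is then about 1 to 3% if the Week 16 response is 60 to 80% of the Week 24 response. That ratio and the even dropout are assumptions, and differential missingness between arms would change the result. The standard error is slightly smaller than the observed data support. The primary and both key secondary endpoints are unaffected. The change is worth making because the rule adds no information, is not reliably conservative, and is easy to remove.

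**What to change.** State in SAP 13.5.4 that the MMRM for HbF and total Hb, as for F-cells (which have no carry-forward rule), uses observed, windowed values only, still excluding values within 56 days of an RBC transfusion. Limit carry-forward to the responder definitions, and align the summary statistics and waterfall plots with whichever value set they are meant to illustrate. If the sponsor keeps the present rule, add an observed-data ITT MMRM as a prespecified sensitivity analysis.

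The cost is about one sentence, ideally before the interim unblinding. No subject leaves the model, because anyone with a carried-forward value already contributes the Week 16 or Week 36 row. The one small downside is that mean-change and responder results would rest on slightly different sets of values; a table footnote can say so.

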10.2 Definitions of Baseline and Change from Baseline Values

Unless otherwise specified, baseline is defined as the last non-missing measurement prior to the first dose of study drug.

All ECG assessments at a visit are to be performed in triplicate at each scheduled visit. The baseline value for ECG parameters will be derived as the average of all non-missing values, at the last visit prior to the first dose of study drug. Post-baseline assessments at a visit will be averaged for analysis.

In analyses of pharmacodynamics (PD) parameters, baseline is defined as the average of non-missing values from the screening and baseline visits. PD assessments include the following laboratory measurements based on blood samples (HbF-associated biomarkers and total Hb; biomarkers of RBC hemolysis, adhesion, inflammation, and cardiac stress; RBC indices).

Change from baseline at a post-baseline visit is defined as follows:

- For the ECG parameters: Post-Baseline Average Value – Baseline Average Value
- For PD parameters: Post-Baseline Value – Baseline Average Value
- For all other parameters: Post-Baseline Value – Baseline Value

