Appendix 3 Schedule of Assessments

| | Screening Period | Baseline | Treatment Period | | | | | | | | | | | | | Follow-up Period |
|---|------------------|----------------|------------------|----|----|----|----|----|-----|-----|-----|-----|-----|-----|-----|------------------|
| | 1 | 2 | 3 | 4 | 5 | 6 | 7 | 8 | 9 | 10 | 11 | 12 | 13 | 14 | 15 | 16 |
| Visit Number | 1 | 2 | 3 | 4 | 5 | 6 | 7 | 8 | 9 | 10 | 11 | 12 | 13 | 14 | 15 | 16 |
| Study Week | -4 to 0 | NA | 1 | 2 | 4 | 6 | 8 | 12 | 16 | 20 | 24 | 30 | 36 | 44 | 52 | EOS 56 |
| Study Day | -28 to -1 | 1 ^a | 7 | 14 | 28 | 42 | 56 | 84 | 112 | 140 | 168 | 210 | 252 | 308 | 364 | 392 ± 7 |
| Administrative Procedures | | | | | | | | | | | | | | | | |
| Informed consent | X | | | | | | | | | | | | | | | |
| Demographic information | X | | | | | | | | | | | | | | | |
| Medical/disease history | X | | | | | | | | | | | | | | | |
| Inclusion/exclusion criteria ^b | X | X | | | | | | | | | | | | | | |
| Randomization | | X | | | | | | | | | | | | | | |
| Telephone visits ^c | | | | X | | X | | | | | | | | | | |
| Safety Assessments | | | | | | | | | | | | | | | | |
| Vital signs ^d | X | X | X | | X | | X | X | X | X | X | X | X | X | X | X |
| Weight | X | X | | | X | | | X | | | X | | X | | X | X |
| Height | X | | | | | | | | | | | | | | | X |
| Physical examination ^e | X | X | X | | X | | X | X | X | X | X | X | X | X | X | X |
| 12-lead ECG ^f | X | X | X | | X | | X | X | X | X | X | X | X | X | X | X |
| Hematology and serum chemistry | X | X | X | | X | | X | X | X | X | X | X | X | X | X | X |
| Coagulation studies | X | | | | | | | X | | | X | | | | | X |
| Urinalysis with urine creatinine, Pr:Cr ratio, and microalbumin | X | X | X | | X | | X | X | X | X | X | X | X | X | X | |

| | Screening Period | Baseline | Treatment Period | | | | | | | | | | | | | Follow-up Period |
|---|------------------|----------------|------------------|-----------|-----------|-----------|-----------|-----------|------------|------------|----------------|----------------|----------------|----------------|------------|--|
| | | | 3 | 4 | 5 | 6 | 7 | 8 | 9 | 10 | 11 | 12 | 13 | 14 | 15 | |
| Visit Number | 1 | 2 | | | | | | | | | | | | | | 16 |
| Study Week | -4 to 0 | NA | 1 | 2 | 4 | 6 | 8 | 12 | 16 | 20 | 24 | 30 | 36 | 44 | 52 | EOS 56 |
| Study Day | -28 to -1 | 1 ^a | 7 ± 2 | 14 ± 3 | 28 ± 5 | 42 ± 5 | 56 ± 5 | 84 ± 5 | 112 ± 7 | 140 ± 7 | 168 ± 7 | 210 ± 7 | 252 ± 7 | 308 ± 7 | 364 ± 7 | 392 ± 7 |

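### The Hb responder endpoint borrows fallback visits and windows built for HbF, so a missing Week 24 or Week 52 Hb can be filled from an older or mislabelled visit depending on visit date

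*SAP*

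**What the plan says.** SAP 13.5.4 states that the Hb responder analysis "will be similar to the HbF responder rate analysis at Week 24 and 52. The same imputation rules will apply". The inherited rules are:

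- For Week 24 (SAP 13.5.3.2.1): "If HbF value is missing at Week 24, the HbF value at Week 16 will be used for the analysis". If Week 16 is missing too, the subject is a non-responder.
- For Week 52 (SAP 13.5.4): "HbF value from Week 36 (the last scheduled visit before the target analysis visit) will be used when Week 52 value is missing".
- In both, values within 8 weeks of a red-cell transfusion are excluded.

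Total Hb is a pharmacodynamic parameter. SAP 10.2 says "PD assessments include the following laboratory measurements based on blood samples (HbF-associated biomarkers and total Hb" and more. The block of Table 2 (SAP 10.5) headed "For all Efficacy (Except for QoL) and PD Analyses" therefore governs it. That block has Weeks 4, 8, 12, 16, 24, 36 and 52 only, for example "Week 16 (Day 112 ± 7) | 100 to 141" and "Week 24 (Day 168 ± 7) | 142 to 211". Windowing comes before any missing-data rule, and the value nearest the scheduled day wins within a window.

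Hb belongs to the hematology panel (SAP 13.5.8.2). The Appendix 3 row that begins "Hematology and serum chemistry | X | X | X" is marked at every on-site visit, including Weeks 20, 30, 44 and 56. The specialty hematology row, which covers HbF and F-cells, is blank at those four visits.

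**The concern.** The reason given for Week 36, that it is the last scheduled visit before the target, is true for HbF and untrue for Hb, whose last scheduled visit before Week 52 is Week 44. For Week 24, the last scheduled Hb visit is Week 20, not Week 16. No Hb-specific window or fallback is given.

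Followed as written, the rule can pass over a measured Hb in favour of one 4 or 8 weeks older, or can count that same measurement as an observed target value. Which happens depends on a one-day difference between two visits that both comply with the protocol. The endpoint is formally tested, as item 10 of the interim list (SAP 12.3) and item 11 of the final list (SAP 12.4). SAP 13.5.4 also carries imputed HbF values into the HbF mixed model and asks for total Hb to be analyzed similarly, so the total Hb model is plausibly reached as well.

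**Working it through.** **Inputs.** Scheduled days (Appendix 3): Week 16 = 112, Week 20 = 140, Week 24 = 168, Week 30 = 210, Week 36 = 252, Week 44 = 308, Week 52 = 364, Week 56 = 392, each ± 7 days. Efficacy windows (Table 2): Week 16 = 100 to 141, Week 24 = 142 to 211, Week 36 = 212 to 309, Week 52 = 310 onward.

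**Reproducing the window limits.** Each upper limit is the midpoint of adjacent efficacy visits plus one day:

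- (112 + 168)/2 + 1 = 141
- (168 + 252)/2 + 1 = 211
- (252 + 364)/2 + 1 = 309

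The same rule gives the earlier limits of 43, 71 and 99. The three midpoints, 140, 210 and 308, are the target days of Weeks 20, 30 and 44. Each cut therefore sits one day after the target day of a visit at which Hb is measured.

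**Where allowed visit days fall (15 days per visit).**

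| Visit | Allowed days | Earlier efficacy window | Later efficacy window | Safety window |
|---|---|---|---|---|
| Week 20 | 133–147 | Week 16: 133–141 (9 days) | Week 24: 142–147 (6) | 128–155 (all 15) |
| Week 30 | 203–217 | Week 24: 203–211 (9) | Week 36: 212–217 (6) | 191–232 (all 15) |
| Week 44 | 301–315 | Week 36: 301–309 (9) | Week 52: 310–315 (6) | 275–337 (all 15) |
| Week 56 | 385–399 | none | Week 52: 385–399 (15) | 380 onward (all 15) |

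**Applying the rules, target Hb missing or excluded.**

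1. Week 16 on Day 112, nothing else in 142–211. With Week 20 on Day 141, Week 16 is nearer to Day 112 (0 against 29 days) and is carried forward. With Week 20 on Day 142, it is the only value in the Week 24 window and counts as observed.
2. Week 36 on Day 252, nothing else from Day 310. With Week 44 on Day 309, Week 36 is carried forward. With Week 44 on Day 310, it counts as Week 52.
3. Week 16 on Day 112, Week 20 on Day 140. With Week 30 on Day 211, the Week 30 value is labelled Week 24 although it is 211 − 168 = 43 days late. With Week 30 on Day 212, Week 16 is carried forward.
4. Week 56 attended on Day 392. It is 28 days from Day 364, and Week 44 on Day 310 is 54 days away. The Week 56 value, taken after treatment has ended, is labelled Week 52 on either side of the Day 309/310 cut.
5. Fallback value (Week 16 or Week 36) also missing. The Week 20 or Week 44 value is used on both sides of the cut, so there is no switch.

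**Illustration (assumed changes).** In case 1, let the change be +0.6 g/dL at Week 16 and +1.3 g/dL at Week 20. Against the 1.0 g/dL threshold, the subject is a non-responder with Week 20 on Day 141 and a responder with it on Day 142.

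**The case against.** The strongest reply is that the one-day switch needs a narrow set of circumstances. A continuing subject with Week 30 on Days 203–211 has a value in the Week 24 window. Early termination visits are eligible for windowing (SAP 10.5), and Protocol 8.4 asks for every effort to complete both the early termination and the end-of-study visits. The Week 52 window is open-ended. All this stands and limits the switch. It does not rescue the rule, because what masks the switch at Week 30 or Week 56 is a value taken 35 to 43 days after the Week 24 target, or one taken off treatment.

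A reader might go further in four ways that the documents do not support:

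- *Applying the SAP's 25% planning dropout to the 115 randomized, giving about 29 affected at Week 52.* A subject who leaves before Week 44 has no Week 44 value to switch, and later leavers often have a value from Day 310 on. The tested comparison also involves about 49 + 31 = 80 subjects, not 115.
- *Reading 9 of 15 and 6 of 15 days as shares of subjects.* They count calendar days only.
- *Taking both fallbacks as justified by the last-scheduled-visit reason.* Only Week 36 is. The Week 16 rule gives no reason.
- *Treating the absence of Weeks 20, 30 and 44 from the mixed models as an error.* A common visit set is a legitimate choice. Going from 7 to 10 visits raises the unstructured covariance from 7 × 8/2 = 28 to 10 × 11/2 = 55 parameters.

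It is also fair to say that visit dates in a blinded trial give no stated reason for bias between arms, so the likely effect is mainly noise.

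**Conclusion.** The point holds in limited form. For the Hb responder endpoint, the inherited fallback visits and efficacy windows do not match the Hb sampling schedule. When the target Hb is missing or excluded, the fallback value is present and no other Hb falls in the target window, a one-day difference at Day 141/142 or Day 309/310 decides whether a measured Hb is discarded or counted as the target. Otherwise a Week 30 value can stand for Week 24, or an off-treatment Week 56 value for Week 52.

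The number of affected subjects and the effect on responder rates cannot be derived from the documents. The primary and key secondary endpoints are not affected. For the HbF responder endpoint this assumes that HbF is available only at the specialty hematology visits, as the SAP has it; Protocol 11.3.6.1 also lists HbF within the hematology panel. This is an inexpensive improvement to a lower-ranked but formally tested endpoint.

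**What to change.** In SAP 13.5.4, give the Hb responder endpoint its own rule instead of a cross-reference:

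- Assign Hb values with windows that include Weeks 20, 30, 44 and 56. Table 2's safety windows already do this, and they end Week 52 at Day 379.
- Name Week 20 as the fallback for Week 24, and Week 44 as the fallback for Week 52. State what happens when the fallback is missing too, since a subject with a Week 16 but no Week 20 value would otherwise change status.
- Where imputed Hb values feed the total Hb mixed model, use the same fallback values.

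With this rule, a Week 20 Hb on Day 141 or Day 142 is used in the same way, as the named fallback. Adding Weeks 20, 30 and 44 as mixed-model visits is optional and not part of the fix.

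The cost is SAP wording, one extra window assignment, and Hb windows that differ from the HbF windows. No new data are needed. The change should be made before unblinding.
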